Because we have prior expectations that the mentorship program will have some degree of success, we don't want to withhold any benefits from the control locals. Thus, we will repeat the mentorship training with control locals in year five of the project. Participation will be voluntary, and no evaluation of the training will be included in this. Rather, it will be a service to the contributing local unions and their members.

Evaluation and Analysis

We have developed the following logic model of the mentorship program to describe our program and provide guidance on necessary evaluation components.

Inputs	Activities	Outputs	Short-term	Intermediate	End Outcomes
			Outcomes	Outcomes	
UW mentorship	Recruit women	Mentor-	Increase in	Reduction in	Reduced
program	apprentices	mentee interact	awareness of	perceived stress	injuries
	and mentors	on regular basis	safety & health		
Sheet Metal			risks	Increase in self-	Improved jobsite
Workers Locals	Online mentor	Mentors provide		advocacy	safety climate
16 and 66	training	emotional,	Increase in self-	behaviors	
programs		appraisal, &	efficacy		Increased
	Matching	informational		Increase in	representation of
CPWR	mentors to	support to	Improved self-	problem-	women in trade
Leadership	mentees	mentees	advocacy	solving skills	
training			knowledge		
programs	Ongoing			Increase in job	
	program		Improved social	satisfaction	
Local union	support		support at work		
engagement				Increased retention	
				in apprenticeship	
				and trade	
PLANNED WORK			RESULTS		

This logic model shows the program inputs and outputs. We will conduct both process and impact evaluations, as described below. We will measure short-term, intermediate term and long-term outcomes, however, we hypothesize that short and intermediate outcomes will be affected by our mentorship program.

Analysis plan

We will conduct a hypothesis-driven analysis of the primary outcome (perceived stress) and a limited set of secondary outcomes that we highlighted as especially important in the grant.

Research question & hypotheses

Primary research question: What is the effect of the mentorship intervention on apprentice's **perceived stress**? Hypothesis: expect a reduction in perceived stress among the intervention group (mentees) compared to controls

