Secondary research questions: What is the effect of the mentorship intervention on the following **short-term and intermediate outcomes**: social support at work, job satisfaction, and intention to leave construction trades? Hypothesis: expect an improvement (increase) in these outcomes among the intervention group compared to controls

Other (process and longer-term health) outcomes we will consider in a second paper where we'll conduct a more exploratory analysis by group:

- Self-reported health
- Self-reported mental health
- Sleep quality
- Sought professional help for mental health
- Sickness presenteeism
- Physical activity outside work
- Insomnia
- Depression severity
- Anxiety severity
- Work/life conflict
- Demand/control
- Overcompensation
- Bullying
- Age discrimination
- Race discrimination

- Gender discrimination
- Tokenism
- Sexual harassment
- Injury at work
- Work injury severity
- frequency of being understood
- perceived effectiveness at communicating
- self-advocacy behaviors
 - formal skills training
 - goal setting
 - perceived progress towards goals
 - perceived ability to advocate for own needs on jobsite

Data

Two control (total n = 40) and intervention (total n = 56) cohorts surveyed at three timepoints each: baseline, 6 months, and 1 year.

Subset of 18 control and 16 mentees who completed surveys at all three timepoints.

Variables to be used in descriptive analysis

Demographics by group:

- Age
- Race/ethnicity

- Marital status
- Family annual income
- Education
- Years in construction industry

Baseline variables by group:

- Mentor experience
- Mentor type
- Formal mentorship training
- Local level mentorship

Variables to be used in primary analysis

Exposure: group – 0 for control, 1 for intervention

Outcome: perceived stress score (continuous)

Fixed effects: time, group x time

Random effect: union local

Covariates: age, race/ethnicity, family annual income, year in apprenticeship, size of local,

region of the country

Variables to be used in secondary analyses

Exposure: group – 0 for control, 1 for intervention

Secondary outcomes: Social support at work (continuous), Job satisfaction (continuous),

Intention to leave construction trades (categorical)

Fixed effects: time, group x time

Random effect: union local

Covariates: age, race/ethnicity, family annual income, year in apprenticeship, size of local,

region of the country

Statistical methods

Software: R

Analysis of loss to follow-up

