Compare those who dropped out to those who stayed in study by:

- Union local [tally]
- Race/ethnicity
- Age
- Marital status
- Dependents
- Stress at baseline
- Years in construction industry
- Intervention status [yes/no]

- Round
- Intention to leave construction industry
- Difficulty taking time off during work to take care of personal or family matters
- Frequency of interference between job demands and family life or personal time
- Frequency of interference between family demands and work

And/or model for loss of follow up to include group, round, plus other vars listed above

Use chi-square test of independence (for discrete variables)/Fisher's Exact test (for count data, small sample sizes)/t-test (for continuous variables)/Wilcoxon rank sum test (for continuous variables not normally distributed)

Bivariate analysis

With same tests as above, compare demographic and other sample characteristics by arm at baseline

With same tests as above, compare primary and secondary outcomes by arm at baseline, midyear, and end-year; also do by round

With same tests as above, do same comparison for subset of respondents in each arm who have surveys at all three timepoints; also do by round

Graph observations (averages, error bars). Spaghetti plots showing trajectories for each person, by group. Stratify by group, explore change btw timepoints. Either paired t-test or single rank Wilcoxon test. First compare BL to MY, then MY to EY.

Multivariate analysis

From research strategy: To evaluate changes over time, effectiveness of the intervention will be analyzed using a mixed effects regression model. For our primary outcome (perceived stress scale, PSS), a base model will be developed with PSS as a function of arm (intervention/control), and survey (pre, 6 months, post), with a random effect for local union (to assess difference between locals, and to control for non-independence within locals). We will then test the contributions of additional co-variates, including demographics, year in apprenticeship, size of local, and region of the country, etc. Co-variates will be retained if they are statistically significant (p<0.1) or change the coefficient for study arm by \geq 10%. Similar models will subsequently be run for each short-term and intermediate outcome.

Table shells -> see SMART Training Program_Survey responses + table shells_17Jun24.xlsx

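### The primary perceived-stress model is written in two unreconciled ways, with no primary follow-up contrast and no participant random effect

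*Combined protocol and SAP*

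**What the plan says.** All references are to the combined protocol and SAP.

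- **Research question & hypotheses** gives no time point: "Hypothesis: expect a reduction in perceived stress among the intervention group (mentees) compared to controls".
- **Data** reports "Two control (total n = 40) and intervention (total n = 56) cohorts surveyed at three timepoints each" and "Subset of 18 control and 16 mentees who completed surveys at all three timepoints".
- **Variables to be used in primary analysis** lists group as the exposure, then "Fixed effects: time, group x time" and "Random effect: union local". It does not say whether time is categorical or numeric.
- **Multivariate analysis** opens "From research strategy: To evaluate changes over time, effectiveness of the intervention will be analyzed using a mixed effects regression model". It then says "a base model will be developed with PSS as a function of arm (intervention/control), and survey (pre, 6 months, post". Local is the only random effect given there, and no interaction appears. A covariate stays if its p-value is below 0.1 or if it moves the arm coefficient by 10% or more. The working list of R steps at the end repeats this.
- **Bivariate analysis** compares the arms at all three surveys and favours none. For within-group change it says "First compare BL to MY, then MY to EY", so baseline is never compared with 1 year.
- **Table 2** is to present the base model and staged covariate models as the effect of the training on perceived stress, without saying which coefficient carries that effect.

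**The concern.** The two descriptions can be combined as arm, survey and arm-by-survey, but no section says so, and a rule about one arm coefficient does not fit that model. What Table 2 reports depends on the reading:

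- **(a) Additive, arm plus survey.** Baseline is one of the averaged surveys, so the arm coefficient mixes a pre-intervention difference with the two later ones.
- **(b) Interaction with a group main effect, baseline as reference.** The arm coefficient is the baseline difference, so the 10% rule watches the wrong quantity.
- **(c) The variable list taken literally, with no group main effect.** Categorical time gives three survey-specific differences and no single arm coefficient. Numeric time gives one slope.

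Under every reading, no follow-up contrast is named and within-person correlation has no term of its own.

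The Data section shows responses in hand, and the working list records that by-arm tests had already been run in cross-tabulations. The choice is therefore open after results can be seen. Mentees were recruited after their local's allocation was known, so a baseline difference between arms is plausible, and reading (a) would carry it into the reported effect.

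**Working it through.** The plan gives no effect size, SD or power figure, so there is nothing of its own to reproduce. The check asks what each reading would report from the same data.

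**Inputs from the plan.** 40 control and 56 intervention women; 18 and 16 completers; 26 locals with five or more women apprentices (the number randomised is not stated).

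**Assumptions.** All 96 have baseline data; SD 1; true effect 0.5 SD at both follow-ups and 0 at baseline; within-person correlation r = 0.5; local ICC 0.05; 12 to 26 locals. Counts per survey are not given, so three loss patterns are used: follow-up in completers only; everyone at 6 months and completers at 1 year; non-completers split evenly between the two follow-ups.

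**1. Additive model, ignoring the local term.** The arm coefficient averages the survey-specific differences with weights w = n0·n1/(n0+n1).
- Baseline: 40×56/96 = 23.33. Completers: 18×16/34 = 8.47.
- Completers only: (2×8.47)/(23.33 + 2×8.47) = 16.94/40.27 = 0.421.
- All at 6 months: (23.33 + 8.47)/(23.33 + 23.33 + 8.47) = 0.577.
- Even split (29 and 36 at each follow-up): w = 29×36/65 = 16.06; 32.12/(23.33 + 32.12) = 0.579.
- Enumerating every loss pattern consistent with 34 completers gives a minimum of 0.421 and a maximum of 0.579. These shares need no assumption about SD, r or ICC.

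**2. Baseline difference carried into reading (a).** For 0.4 SD, the direct part is 0.4×(1−0.579) to 0.4×(1−0.421) = 0.17 to 0.23 SD. If half persists at follow-up, the weights are 0.711 to 0.790, giving 0.28 to 0.32 SD.

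**3. The other readings.** Arm-by-1-year is 0.5 − 0 = 0.5 SD. With numeric time and no group main effect (completers only, local ignored), the slope is (1×0.5 + 2×0.5)/(1² + 2²) = 0.30 per survey, or 0.60 SD projected to 1 year.

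**4. REML simulation with a local effect** (12, 18 and 26 locals; three loss patterns; 3,000–4,000 replicates per cell).

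| Reading | Reported for a true 0.5 SD |
|---|---|
| Additive arm coefficient | 0.19–0.30 (38–59%) |
| Arm-by-1-year, categorical | 0.49–0.51 |
| Numeric slope × 2, no group main effect | 0.57–0.71 |

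**5. No participant effect, arm-by-1-year, completers only.** By hand, ignoring clustering: the variance treated as independent is 1/23.33 + 1/8.47 = 0.161, SE 0.40. The actual variance subtracts 2r/23.33 = 0.043, leaving 0.118, SE 0.34. In simulation:
- Local only: model SE 0.38–0.39 against actual 0.34; null rejection 2.4–3.3%; power for 0.5 SD 23–24%.
- Local and participant: model SE 0.31 against actual 0.31–0.32; null rejection 4.9–5.8%; power 35–37%.

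For the additive model with 26 locals, the SE is 0.178 against 0.213 if local variance is held at ICC 0.05. When REML estimates it (12–26 locals), the local term absorbs part of the participant variance and the gap mostly closes (0.21–0.23 against 0.21–0.24).

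**6. The 10% rule under reading (b)** (26 locals, 3,000 replicates per cell). A pure-noise covariate moves the baseline-difference coefficient by 10% or more in 32–36% of trials when the true baseline difference is 0, 24–28% at 0.2 SD and 11–14% at 0.4 SD. Keyed to arm-by-1-year with a participant effect, it fires in 1–8%.

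**The case against.** - **The additive text may be carried over.** It is labelled as coming from the research strategy, and its stated aim of studying change over time suits an interaction. But it is the only account of model building in the plan, it appears twice, and nothing marks it as superseded.
- **Reading (c) is strained.** Group is listed as the exposure just above the fixed effects, and time is always described as labelled surveys. Dropping the group main effect with categorical time only reparameterises the same model. The 0.6–0.7 SD figure needs two unlikely choices together and should carry little weight. The spread of 0.2–0.3 against 0.5 stands without it.
- **Other files might settle it.** Table shells and variable coding sit in separate files that are not part of the public document. They cannot be assumed to fix the model, and the public text conflicts with itself.
- **Omitting the participant effect does limited harm to error rates.** It leaves arm-by-1-year unbiased and conservative. For the additive coefficient, simulated null rejection was 5.4–6.9% with local only. That is right: the cost is mainly power and wrong error bars, not gross false positives.
- **The 10% rule fires often but moves little.** When a noise covariate triggered it, arm-by-1-year shifted by 0.02 SD on average, against an SE near 0.35, and Table 2 also shows the base model. This stands: the defect is a rule keyed to the wrong coefficient, not a large bias.
- **The paired tests are within-group exploration.** Agreed; they neither supply the primary contrast nor contradict one.

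**Conclusion.** The concern holds: the primary analysis is wrong as written, not merely short on detail. Followed literally, the text leads to a diluted additive coefficient or to a covariate rule keyed to the baseline difference. Either way, no primary contrast is named and repeated surveys on the same woman have no term of their own. The firmest figure is the 42–58% recovery under the additive reading, which rests only on the plan's counts, complete baseline data, an effect equal at both follow-ups and ignoring the local term. 42% is the floor over all loss patterns. The simulated standard errors and power also depend on the assumed r, ICC and number of locals. A separate simulation with 10 locals per arm and about 30% of non-completers giving one follow-up survey agrees: additive estimate 0.23, arm-by-1-year SE 0.36 against actual 0.33, and power 24% rising to 39% with a participant effect. Dilution and baseline carry-over apply only to reading (a); the missing contrast and missing participant effect apply to all. Because outcome data have already been examined by arm, this should be settled before Table 2 is reported.

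**What to change.** State one primary model identically in the variable list, the Multivariate analysis section and the working list: perceived stress on arm, categorical survey and arm-by-survey, with random effects for local and for participant. Follow-up stress adjusted for baseline stress, with the same random effects, is an acceptable alternative. Name one primary contrast, for example arm-by-1-year or the mean of the two follow-ups. Report it with a 95% CI and treat the other time as secondary. Tie the 10% rule to that contrast, bring the table shells into line, and disclose that the choice was made with data in hand; it cannot be presented as blind pre-specification.

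Make the interaction and participant changes together. A participant effect added to the additive model alone lowers the recovered share to 31–32% (completers only).

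The cost is wording, two interaction terms and one random effect, with no new data. The named contrast has a larger SE than the additive coefficient (about 0.31 against 0.21 SD; completers only, 26 locals). Because it is not diluted, its simulated power for 0.5 SD is still higher: 35–37% against 16–18% with completers only, and 35–57% against 16–35% over the three loss patterns. Power stays modest either way.

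### The mixed models carry a random effect for union local but none for the woman, so a group x time test, if that is the primary test, is conservative and loses power

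*Combined protocol and SAP*

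**What the plan says.** The Data paragraph of the Analysis plan describes 40 control and 56 intervention women surveyed at baseline, 6 months and 1 year. It also reports a "Subset of 18 control and 16 mentees who completed surveys at all three timepoints".

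The variable lists for the primary and for the secondary analyses both give "Fixed effects: time, group x time" and "Random effect: union local". No other random effect is listed.

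The Multivariate analysis section gives the fixed part of the base model as "PSS as a function of arm (intervention/control), and survey (pre, 6 months, post"). The same sentence then names the only random term in that model: "with a random effect for local union (to assess difference between locals, and to control for non-independence within locals"). The working list of analytic steps at the end repeats this with the same single random effect. Neither prose description contains an interaction.

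The only later additions described are covariates, entered in stages (Tables 2 and 3 in the table shells) and kept under this rule: "Co-variates will be retained if they are statistically significant (p<0.1") or if they shift the arm coefficient by at least 10%. Secondary outcomes get similar models; one of them is "Intention to leave construction trades (categorical").

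Pairing within a woman is used only in the Bivariate analysis section, for change within each arm: "Either paired t-test or single rank Wilcoxon test".

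**The concern.** A random intercept for local handles likeness between women of the same local, which is the purpose the plan states for it. It does not handle the stronger likeness between one woman's own surveys. No section adds a participant effect, a within-person residual correlation, GEE or robust standard errors. A model fitted in R as written, with default independent residuals, treats two surveys from one woman as no more alike than surveys from two women in her local.

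Group x time is a within-woman contrast: a woman's stable level cancels when her later score is compared with her baseline. A model that cannot see this leaves the stable level in the residual. With 96 women, and only 34 (18 + 16) with all three surveys, the lost precision could make a real benefit look like no effect.

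A smaller matter is covariate selection. For covariates fixed within a woman, such as race/ethnicity, the same omission makes the standard error too small, so the p<0.1 rule keeps irrelevant ones too often.

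**Working it through.** The documents give no power calculation, SD, effect size or within-woman correlation, so there is no planned figure to reproduce.

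**Inputs from the documents:** arms of 40 and 56; three surveys; 18 and 16 complete; 26 locals with five or more women apprentices (Recruitment and Assignment of Locals). The number of locals enrolled is not given.

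**Assumed:** 13 locals per arm, total variance 1, local share 0.05, woman share 0.20 to 0.65, residual share the remainder, true effect 0.5 SD at 1 year, two-sided 5% test.

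**Step 1: complete data by hand, woman share 0.50.** The residual share is 1 − 0.05 − 0.50 = 0.45.
- With a participant term: SE = sqrt(2 × 0.45 × (1/40 + 1/56)) = 0.196.
- With all woman variance left in the residual: sqrt(2 × 0.95 × (1/40 + 1/56)) = 0.285. The fitted local-only model gives 0.272, because the local term absorbs some of that variance.
- Ratio: 0.272/0.196 = 1.39. At shares 0.35 and 0.65 it is 1.22 and 1.67.

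**Step 2: with dropout.** Random monotone dropout, leaving on average 18 and 16 completers (simulation, 1,300 runs per share):

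| Woman share | SE, local only | SE, local + participant | Ratio | Power, local only | Power, local + participant | Null rejection, local only |
|---|---|---|---|---|---|---|
| 0.35 | 0.387 | 0.335 | 1.15 | 22% | 32% | 2.4% |
| 0.50 | 0.382 | 0.297 | 1.29 | 20% | 39% | 1.5% |
| 0.65 | 0.376 | 0.247 | 1.52 | 20% | 53% | 1.1% |

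The power with the participant term can be checked by hand. At share 0.50, 0.5/0.297 − 1.96 = −0.28, and Φ(−0.28) = 39%. At a woman share of 0.20 the comparison is only 23% against 27%.

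A separate calculation with a different dropout pattern, at share 0.50, gives a reported local-only SE of 0.371, a true SE of 0.331 for that estimator, and 0.293 with the participant term. From these:
- Local-only power: Φ((0.5 − 1.96 × 0.371)/0.331) = Φ(−0.69) = 25%, against 40% with the participant term.
- Local-only null rejection: 2 × Φ(−1.96 × 0.371/0.331) = 2.8%.

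So the loss has two sources: the reported SE is too large, and with missing surveys the estimator is also less efficient.

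**Step 3: if the arm main effect is the test.** The local-only SE is 1.01 to 1.05 times the SE with the participant term, and simulated null rejection is 4.9% to 6.5%. The loss in Step 2 does not carry over.

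**Step 4: if locals also vary over time.** With local-by-time variance 0.05 (assumed), woman share 0.50 and dropout, power is about 24% for the local-only model against 34% with the correct covariance. Rejection of a true null at that variance, over woman shares 0.35 to 0.65:

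| Model | With dropout | Complete data |
|---|---|---|
| Local only | 3.3% to 4.3% | 1.8% to 4.5% |
| Local + participant | 7.8% to 10.2% | 10.0% to 12.3% |
| Plus local-by-time effect | 6.0% to 6.2% | 4.8% to 5.5% |
| Small-sample-corrected clustered SEs | 5.7% to 5.8% | 4.5% to 4.8% |

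At variance 0.02 with dropout, the local + participant model rejects in 5.5% to 6.3% of runs.

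**Step 5: covariate rule.** With dropout, a woman-fixed covariate with no effect passes p<0.1 in 21% to 26% of runs under the local-only model, and in 11% to 12% with the participant term.

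The categorical outcome was not simulated.

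**The case against.** Four objections have weight.

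- **The interaction may not be the test.** It appears only in the variable lists. Both prose descriptions give arm and survey, and the covariate rule follows the arm coefficient. This stands: the power loss is conditional on the contrast, and the plan has to say which it is.
- **The participant term alone may be too liberal.** Locals are randomized, and Step 4 shows inflated rejection if local-by-time variance exists. This stands too, and the fix must cover it. It does not rescue the local-only model, whose caution is an accidental by-product of misplaced variance.
- **The size is assumed.** It is. The gain nearly vanishes at a low woman share, but the local-only model had less power in every group x time setting calculated.
- **The residual structure is merely unstated, and the last section is a working note.** This is partly fair. But the variable lists are unhedged, and the only additions described are covariates, so a model fitted as written would omit the woman.

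Two stronger readings are tempting. A reader might infer that ignoring repeated surveys produces false positives for the intervention. For group x time the error runs the other way, and for the arm term little changes. A reader might also infer that dropout biases the local-only estimate. That would need dropout related to stress, differently by arm, and the documents do not show this.

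**Conclusion.** The omission is real and should be fixed. If group x time is the test and residuals are independent, the planned model is conservative (about 1% to 3% null rejection with dropout at woman shares 0.35 to 0.65, without local-by-time variance). It has about 20% to 25% power, against 27% to 53% with a participant term, for an assumed 0.5 SD effect and woman shares of 0.20 to 0.65. Local-by-time variation narrows the gap. If the arm main effect is the test, little is lost on the treatment comparison.

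The direction for group x time follows from the structure of the contrast. The size depends on the assumed variances, effect, number of locals and dropout pattern. The same omission applies to the secondary models, but its size for intention to leave is not known.

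**What to change.** 1. In both variable lists, the Multivariate analysis section and the working list, specify random intercepts for union local and for participant nested in local. For perceived stress, social support and job satisfaction, fit by REML with Kenward-Roger or Satterthwaite degrees of freedom. For intention to leave, use the same two intercepts in a generalized or ordinal mixed model.
2. Reconcile the variable lists (group x time) with the prose (arm and survey), and name one primary contrast.
3. Because locals are randomized (Approach, Overview), report the group x time test also with a local-by-time random effect or with small-sample-corrected local-clustered standard errors. Do not claim an effect that holds only without that protection.
4. Apply the p<0.1 covariate rule only in the model that contains the participant term.

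The cost is one model term, a few lines of text and one sensitivity analysis, with no new data. The local variance may be estimated as zero (16% to 31% of the simulated two-intercept fits without local-by-time variance). In that case, keep the participant term and report the zero estimate. The working list shows that some group comparisons have already been run, so date and document the change.

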Table 1: Baseline characteristics of participants (n=X), by study arm [+ outcomes at baseline for descriptives, may not use]

Table 2: Effect of mentorship training on level of perceived stress among tradeswomen using mixed effects regression models; base model + models with added covariates, in stages

Table 3: Effect of mentorship training on [X secondary outcomes] among tradeswomen using mixed effects regression models; base model + models with added covariates, in stages

Notes

Keep track of remaining tasks and questions here. Update with steps taken and info obtained as tasks are completed.

Survey data

Estimated missingness for each variable.

Filled in sources as best as I could in scale source doc.

Data dictionary – For scores that we modified, proposed strategy (mostly should just be average score, but noted any alternatives reported in the literature, e.g. if others that are unaltered but just subset of questions and whether others have done that, whether they standardized the scale to the original i.e. by multiplying total by old max divided by new max).

SMART Women_Variable info – summarizes variables we plan to analyze, their type (demographic/confounder, outcome, mediator) and how they'll be categorized.

Working list of analytic steps to do in R

Conduct descriptive analysis of demographic characteristics by study arm (intervention/control) using relevant statistical test. Also check balance in terms of year in apprenticeship, size of local, and region of the country.

Analysis of loss to follow-up:

- Union local size [tally cioè of n ppl in local?]
- Race/ethnicity
- Age
- Marital status
- Dependents [y/n]
- Stress at baseline
- Years in construction industry
- Intervention status [group]
- Round
- Intention to leave construction industry
- Difficulty taking time off during work to take care of personal or family matters
- Frequency of interference between job demands and family life or personal time
- Frequency of interference between family demands and work

Visualize outcomes by group at each time point --> did this implicitly by running tests automatically in crosstables. If outcomes not normally distributed, compare groups at each timepoint (not differences) using Wilcoxon ranksum test (rather than two sample t-test). Complete responses. Will tell us if have group diffs at each timepoint.

once have dates, edit code and add to plots by round (all data, complete responses)

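### If any woman-level covariate has missing values, the staged models and the 10% rule would compare arm coefficients from different sets of women

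*Combined protocol and SAP*

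**What the plan says.** Under Statistical methods, Multivariate analysis, "a base model will be developed with PSS as a function of arm (intervention/control), and survey", with a random effect for the local. Further covariates are then tried: "Co-variates will be retained if they are statistically significant (p<0.1) or change the coefficient for study arm by" at least 10%. The last paragraph of the Notes repeats this, and similar models follow for the other outcomes.

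The list under Variables to be used in primary analysis reads "Covariates: age, race/ethnicity, family annual income, year in apprenticeship, size of local", followed by region. Four of these six belong to the woman and two to the local. The same section also names a group-by-time term, which the base model described under Multivariate analysis does not have.

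The table shells for Tables 2 and 3 show "base model + models with added covariates, in stages".

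On blank items, the only text is a line under Notes, Survey data: "Estimated missingness for each variable". The document gives no rates, no complete-case or imputation rule, no common sample across stages and no count per model. The loss-to-follow-up analysis concerns women who left the study and sets no rule for a blank covariate. The software is R, with no statement about incomplete rows.

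**The concern.** A change-in-estimate rule can be interpreted only if both coefficients come from the same rows. R's model functions usually delete any row with a missing covariate. If, say, some women left income blank, the base model would include them and the income-adjusted model would not. The difference between the two coefficients would then mix two things: adjustment for income, and the removal of those women. The plan would read all of it as confounding and might keep the covariate for that reason alone.

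The columns of Tables 2 and 3 would invite the same misreading. The most adjusted column would also leave out enrolled women who had answered the outcome questions. That costs precision and, if non-response is related to stress, could add selection.

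**Working it through.** The documents give no missing-data figure, effect size or SD, so there is no figure of the plan's own to reproduce. The check asks how far row loss alone can move the arm coefficient.

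**Inputs from the document (Data section)**
- "Two control (total n = 40) and intervention (total n = 56) cohorts": 40 + 56 = 96 women.
- "Subset of 18 control and 16 mentees who completed surveys at all three timepoints": 18/40 = 45% of controls, 16/56 = 29% of mentees, 34/96 = 35% overall.

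**Assumed inputs**
- Missing rate of 2% to 20% per covariate, unrelated to arm or outcome.
- True differences of 0.2, 0.3, 0.5 and 0.8 SD. The plan gives only a direction: "expect a reduction in perceived stress among the intervention group (mentees) compared to controls".

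**Step 1: spread of the shift.** For a simple two-group comparison, the standard error of the arm difference is sqrt(1/40 + 1/56) = 0.207 SD. If a fraction m of women is lost at random, the shift in the coefficient has SD 0.207 × sqrt(m/(1−m)):
- m = 2%: 0.030 SD
- m = 5%: 0.047 SD
- m = 10%: 0.069 SD
- m = 20%: 0.104 SD

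At a true difference of 0.3 SD, the 10% mark is a move of only 0.03 SD. The shift expected from losing 2% of women is already about that large.

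**Step 2: how often the mark is passed.** A simulation of the 40 versus 56 comparison (20,000 runs per cell) removed women at random, added no covariate, and counted moves of at least 10% of the full-sample estimate.

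| True difference | 2 women lost | 5 lost | 10 lost | 19 lost |
|---|---|---|---|---|
| 0.2 SD | 49% | 64% | 75% | 82% |
| 0.3 SD | 38% | 55% | 67% | 77% |
| 0.5 SD | 17% | 34% | 49% | 63% |
| 0.8 SD | 3% | 13% | 28% | 45% |

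**Step 3: clustering and repeated surveys.** The exercise was repeated with a random intercept for local and up to three surveys per woman. Assumptions: 20 locals, local variance fixed at 0.05, woman-level variance 0.5 of a total of 1, dropout matched to 18/40 and 16/56, and 1,500 runs per cell. With 2, 5 or 10 women lost, the mark was passed 34%, 51% or 63% of the time at 0.3 SD, and 15%, 31% or 47% at 0.5 SD. These are close to Step 2, so ignoring clustering and repeats does not drive the result.

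**Step 4: women left in the fully adjusted model.** With gaps occurring independently in each of the four woman-level covariates, the number kept is 96 × (1−m)^4:
- m = 2%: 96 × 0.922 = about 89
- m = 5%: 96 × 0.815 = about 78

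Local size and region are left out of this count because they describe the local and should rarely be missing.

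**Step 5: with a common sample.** If every stage uses the same rows, the shift from lost rows is zero by construction. Imputing the covariates keeps all 96 women.

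**The case against.** The strongest reply is that the documents do not show that any covariate has a gap. Recording that missingness was estimated does not say that some was found, or in which variable. A reader might infer that the adjusted result does rest on fewer women. That does not follow, because it needs both missing values and deleted rows, and the plan states neither. This stands, and the point is conditional for that reason.

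A reader might also infer that randomised women would be discarded. Under Recruitment and Assignment of Locals, it is the locals that are randomised; women are recruited afterwards. What would be lost is enrolled women with outcome data.

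The size depends on the assumptions. Across the effects and losses tried, the chance of passing the 10% mark runs from 3% to 82%, so no single figure can be attached to this trial. Gaps that fall in the same women would remove fewer than Step 4 suggests.

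The base model is still printed and loses no rows to covariates. If the covariate list were fixed in advance, the 10% rule would decide nothing, and only the unequal numbers between columns would remain. Incomplete surveys, with 34 of 96 women completing all three, are the larger documented loss. The table-shell workbook and variable-information file, which the document cites but does not reproduce, might show counts per model or a missing category. All of this limits the weight of the point. It does not supply the missing rule, and counts alone would not make the columns comparable.

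**Conclusion.** The point holds in conditional form. The plan compares arm coefficients across staged models under a 10% rule, with nothing to keep the sample constant. If even a few women lack a woman-level covariate and R deletes their rows, chance row loss can often pass the 10% mark at small to moderate effects. For 2 to 10 women lost, that is about 38% to 67% of the time at 0.3 SD, 17% to 49% at 0.5 SD and 3% to 28% at 0.8 SD. Missing rates of 2% to 5% in each of the four covariates would leave about 89 to 78 of 96 women.

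These figures assume values missing unrelated to arm and outcome; gaps related to either could add bias. They describe a single arm coefficient in a model without the interaction. With the group-by-time term included and baseline as reference, the arm coefficient is the baseline difference, so the plan must also say which coefficient the 10% rule applies to.

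This is a cheap improvement to make before the models are relied on. It is not evidence that a result is wrong.

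**What to change.** Add to the Multivariate analysis section:
- State the amount missing for each covariate, by arm.
- Impute missing baseline covariates from the other baseline variables before modelling, and describe the imputation model.
- Fit the base model and every staged model to the same women and the same surveys.
- If the 10% rule is kept, apply it only between models fitted to identical rows, and name the coefficient it refers to given the group-by-time term. Fixing the covariate list in advance would remove the need for the rule.
- Print the number of women and of surveys in each column of Tables 2 and 3.

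Because women were recruited after their local was assigned, covariate balance between arms is not assured. A separate missing category is therefore a less safe substitute for imputation.

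The cost is a few sentences and a short extra step in R, with no new data. The downside is reliance on an imputation model for what may be a few values. If there are no gaps, the only change is the printed counts and the definition of the coefficient.
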